8.2.1 Screening Procedures

8.2.1.1 VISIT 1

The screening visit will take place within 3 days prior to Visit 2. After obtaining informed consent, site staff will perform/assess the following procedures in the order below. There will be a collection of information including:

- Demographics
- Prior documented DED diagnosis
- Ocular, general medical and surgical history
- Concomitant medication history
- UPT for all eligible WOCBP
- BCVA assessment
- Unanesthetized STT
- Dilated Ophthalmoscopy
- Assessment of ocular lubricant self-instillation
- AE assessment

- Inclusion and exclusion criteria assessment: Subjects who do not meet the evaluated criteria will not continue participation in the study. Any subject who does not meet eligibility requirements will be considered a Screen Failure.

Subjects should be reminded not to use artificial tears or any other OTC or prescription or any other topical eye medication except for the IP for the duration of their participation in the study.

Subject will be scheduled to return for Visit 2 in one to three days.

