9.2 Adverse Event Descriptors

9.2.1 Intensity/Severity Categorization

The term "severe" is often used to describe the intensity (severity) of a specific event (as in mild, moderate, or severe myocardial infarction); however, the event itself may be of relatively minor medical significance (such as severe headache). This is not the same as "serious," which is based on subject/event outcome or action criteria usually associated with events that pose a threat to a subject's life or functioning. Seriousness (not severity) serves as a guide for defining regulatory reporting obligations.

In general, the intensity of a particular AE to be recorded is the worst intensity experienced by the subject during the course of the event. The medical assessment of intensity will be determined by using the following definitions:

- Mild: The AE is easily tolerated and does not interfere with usual activity.
- Moderate: The AE interferes with daily activity, but the subject is still able to function.
- Severe: The AE is incapacitating, and the subject is unable to work or complete usual activity.

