9.3 Reporting Procedure for AEs, SAEs, and Pregnancy

9.3.1 Adverse Events

All AEs observed from time of signing of the ICF will be recorded in the subject's source documentation. This applies to all AEs regardless of presumed relationship to the study drug. For screen failure subjects, any AEs and SAEs occurring during the screening period (after informed consent) will be recorded in the subject's source documentation only and will not be collected on the eCRF. Adverse events leading to discontinuation of study drug must be collected.

If any AE is reported, the date of onset, relationship to disease under study, relationship to study treatment, any action taken, date of resolution (or the fact that it is still continuing or has become chronic), outcome, and whether the AE is serious or not, will be recorded. Use of colloquialisms and abbreviations should be avoided. Only one AE term should be recorded in the event field on the AE eCRF. Where possible, the Investigator should report a diagnosis rather than signs and symptoms or abnormal laboratory values. However, if a constellation of signs and/or symptoms cannot be medically characterized as a single diagnosis or syndrome at the time of reporting, each individual event should be recorded on the AE eCRF. If a diagnosis is subsequently established, all previously reported AEs based on signs and symptoms should be nullified by the Investigator and replaced by one AE report based on the single diagnosis, with a starting date that corresponds to the starting date of the first symptom of the eventual diagnosis.

The AE reporting period begins at the time the ICF is signed by the subject. For screen failure subjects, any AEs and SAEs occurring during the screening period will be recorded in the subject's source documentation only. For enrolled subjects (i.e., those who successfully complete screening), the AE reporting period ends at the Follow-Up visit (Visit 6). Adverse events persisting at the time of study completion will be followed by the Investigator through contact with the subject until resolution or stabilization has occurred (or the subject is lost to follow-up and cannot be contacted) and recorded in the source documents. If the subject reports

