3.2.5 Treatment-Emergent Adverse Event (TEAE)

A treatment emergent adverse event (TEAE) is defined as any AE that has an onset on or after the first dose of IP/study drug and on or before the last dose of IP/study drug plus 3 days.

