8.0 SAFETY EVALUATIONS

8.1 Adverse Events

For screen failure subjects, any AEs and SAEs occurring during the screening period (after informed consent) will be recorded in the subject's source documentation only and will not be collected on the eCRF.

For enrolled subjects, all AEs and SAEs will be recorded in the AE section of the subject's eCRF and source documentation.

A treatment emergent adverse event (TEAE) is defined as any AE that has an onset on or after the first dose of IP/study drug and on or before the last dose of IP/study drug plus 3 days. Only treatment-emergent events will be summarized. All events in the clinical database regardless of when they occurred will be provided in data listings i.e., for enrolled subjects, data listings will have screening AEs/SAEs and TEAEs/serious TEAEs. Adverse events will be presented by Medical Dictionary of Regulatory Activities (MedDRA) primary system organ class (SOC) and preferred term (PT).

An overall summary will be presented which gives the number and percentage of subjects within each treatment group (n (%)), and the number of events (E) that experienced:

- Any TEAE
- Any Treatment-Related TEAE
- Any Disease-Related TEAE
- Any Serious TEAE
- Any Serious Treatment-Related TEAE
- Any Serious Disease-Related TEAE.
- Any TEAE Leading to Study Drug Discontinuation
- Any Treatment-Related TEAE Leading to Study Drug Discontinuation
- Any Disease-Related TEAE Leading to Study Drug Discontinuation
- Any TEAE with Outcome of Death
- Any Treatment-Related TEAE with Outcome of Death
- Any Disease-Related TEAE with Outcome of Death

In summary tables, ocular AEs recorded once for each eye separately but in the same timeframe will be summarized once at the greater intensity and relationship to study drug. The number and percentage of subjects experiencing one or more events within a MedDRA SOC and PT class without regard to intensity, relationship, or seriousness will be tabulated by treatment group. Additional tables for TEAEs and Serious TEAEs will display events by SOC, PT, and maximum intensity.

The following Adverse Event listings will be provided:

- Listing of TEAEs by treatment group ordered by subject, SOC, PT, and date (study day)
- Listing of serious TEAEs by treatment group ordered by subject, SOC, PT, and onset date (study day)
- Listing of TEAEs leading to study drug interruption or discontinuation
- Listing of TEAEs resulting in death
- Listing of all AEs not classified as Treatment Emergent

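### The onset-only TEAE rule leaves out of the AE summary tables an event that opens before first dose and worsens on drug, and a diagnosis back-dated to a pre-dose symptom

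*SAP*

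**What the plan says.** The definition appears twice in the SAP. Section 3.2.5 counts "any AE that has an onset on or after the first dose of IP/study drug" and closes the period with "on or before the last dose of IP/study drug plus 3 days". Section 8.1 repeats the rule ("A treatment emergent adverse event (TEAE) is defined as any AE that has an onset on or after the first dose of IP/study drug") and adds "Only treatment-emergent events will be summarized". Everything else goes to data listings, among them a "Listing of all AEs not classified as Treatment Emergent". Neither section mentions an event that was present before dosing and became worse.

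Three protocol rules bear on which onset date an event carries:

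- Section 9.3.1 starts AE collection when consent is signed, so a randomized subject can have an AE open before the first dose.
- Section 9.2.1 (repeated in SAP 3.2.6) states that, in general, "the intensity of a particular AE to be recorded is the worst intensity experienced by the subject during the course of the event". It does not tell the site to open a new record when an event worsens.
- Section 9.3.1 also covers a diagnosis reached later. The symptom-level AEs are nullified and one diagnosis replaces them, "with a starting date that corresponds to the starting date of the first symptom of the eventual diagnosis".

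Protocol 9.2.4 and SAP 3.2.9 deal with symptoms of the disease under study. Ordinary daily variation is not an AE. Worsening is recorded as one, either flagged as worsening or given the worst intensity seen.

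**The concern.** Eyes are handled several times before the first dose. Visit 1 includes Schirmer strips, a dilated examination and the step listed as "Assessment of ocular lubricant self-instillation". The pre-randomization part of Visit 2 adds a second lubricant drop and fluorescein. An ocular AE can therefore already be open when study drug starts.

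If such an event becomes worse on drug, or becomes serious, the natural place to see it is the AE table by arm. Under an onset-only rule it is classified by the date it began, and what happened after dosing plays no part. The maximum-intensity and drug-discontinuation summaries are restricted to TEAEs too, so they would miss it as well. The trial asks how well a drop is tolerated, and aggravation of an existing event is one of the ways poor tolerability can show.

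**Working it through.** The plan states no figure on this point, so the check applies the written rule to cases and traces where each one is reported.

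**Inputs.** First dose is Day 1 and there is no Day 0 (SAP 7.1). Treatment lasts 28 days. Visit 1 falls one to three days before Visit 2 (Protocol 8.2.1.1). There are about 45 subjects per arm (Protocol 5.1).

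**Rule as written.** An AE is a TEAE if Day 1 ≤ onset ≤ last dose + 3 days. With a last dose on Day 28 the period is Day 1 to Day 31.

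| Case | Onset used | Written rule | With a worsening clause |
|---|---|---|---|
| One record, begins Day -2, worsens Day 3 | Day -2 | not a TEAE | TEAE |
| Diagnosis on Day 5, dated back to a Day -1 symptom | Day -1 | not a TEAE | TEAE |
| Worsening entered as its own AE on Day 3 | Day 3 | TEAE | TEAE |
| New event on Day 1 after the first dose | Day 1 | TEAE | TEAE |

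The first and third rows describe the same clinical course. Their classification differs only because of how the site filled in the form. The second row goes further: any symptom AE already recorded after dosing would be nullified, so an event that counted stops counting.

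**Where the two excluded cases are reported.** SAP 8.1 restricts the overall summary (including related, serious and discontinuation rows), the SOC/PT table and the maximum-intensity tables to TEAEs. Its listings of serious events and of events leading to interruption or discontinuation are also restricted to TEAEs. Only the listing of non-treatment-emergent AEs holds these cases. SAP 7.2, by contrast, tabulates reasons for stopping study medication for all randomized subjects without that restriction. Its count of stops for an intolerable AE could therefore exceed the count in the AE discontinuation table.

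**Comparison with the SAP's other conventions.** Under SAP 6.2, an event with no start date that is still ongoing, or that ends on or after first dose, is given the first-dose date and so counts. The same event with a known Day -2 start that then worsens does not count.

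**Size.** One subject is 1/45 = 2.2 percentage points of an arm, two are 4.4 and three are 6.7. The any-TEAE row moves only if the subject has no other TEAE. The share of subjects affected, p, is not in the documents, so the values below are assumptions. Expected number per arm is 45p, and the chance of at least one among 90 subjects is 1 − (1 − p)^90.

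| Assumed p | Expected per arm | Chance of at least one in 90 |
|---|---|---|
| 1% | 0.45 | 0.595 |
| 3% | 1.35 | 0.936 |
| 5% | 2.25 | 0.990 |
| 10% | 4.5 | more than 0.99 |

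**The case against.** The best defence is that the documents already catch most of what matters.

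- **Dry eye symptoms.** Protocol 1.1 lists irritation, burning, ocular pain and itching among the symptoms of the disease. Under Protocol 9.2.4, mild irritation at Visit 1 would usually not be an AE at all. Its worsening after dosing is to be recorded as one, and if entered with its post-dose onset it is a TEAE. This largely stands. What remains is that the section also allows worsening to be marked by worst intensity, which leaves the onset date unclear, and that it does not reach other AEs.
- **Recording.** Section 9.2.1 is a grading convention and does not forbid a new record. That is correct, but nothing requires one either, so classification depends on site habit.
- **Opportunity.** The pre-dose window is short. Current conjunctivitis, recent or current ocular infection or inflammation, and lubricant discomfort scores of 30 or more are grounds for exclusion. An event that starts at Visit 2 before dosing carries the Day 1 date and may count if classification uses the date only. All of this makes affected events few. It does not correct the rule.

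Three stronger readings are tempting and are not supported. A reader might infer that such events vanish from all safety output. They do not: slit-lamp, ophthalmoscopy and acuity summaries do not depend on TEAE status, and the event is still listed. (Normal/Abnormal shift tables cannot, however, show worsening from an abnormal baseline.) A reader might infer that the tolerability result is compromised. The Drop Discomfort and symptom VAS analyses are also independent of TEAE status. And a reader might size the loss from the 17% ocular burning in the comparator's package insert, about 8 of 45 (0.17 × 45 = 7.65). That figure is an incidence on drug, mostly describing events the rule already counts, and it says nothing about the share of pre-existing events that worsen.

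**Conclusion.** The point holds as a gap in the AE summaries. The onset-only definition, together with single-record grading at worst intensity and back-dating of diagnoses, misclassifies two kinds of event that belong in the tables by arm. No other section repairs this for AEs outside the disease under study.

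The likely size is small and cannot be estimated from the documents. It is about 2.2 points per affected subject in the any-TEAE row, on the assumption of 45 per arm and no other TEAE in that subject. It might be inferred that more events are lost from the less tolerable arm. The direction is plausible, because pre-dose AEs should be balanced by randomization and the arm that aggravates more of them loses more. The documents give no basis for putting a number on that difference. The primary endpoint is untouched. The change is worth making because the rule gives a wrong classification and correcting it is cheap.

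**What to change.** In SAP 3.2.5 and 8.1, keep the present rule and add two sentences:

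1. An AE that began before first dose is also treatment-emergent if it increases in intensity or becomes serious between first dose and three days past the last dose.
2. A diagnosis that has replaced earlier symptom records is classified by its first post-dose symptom or worsening, not by the back-dated start. The back-dated start stays in the listings.

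Add one line to the eCRF completion guidelines, which Protocol 13.1.1 already provides for: post-dose worsening is entered with its own date, and that date is retained when symptom records are nullified. Without it, the second sentence cannot be programmed. If a site enters worsening as a separate AE, that record already qualifies, and the original record should not be counted again in the number of events.

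The cost is two SAP sentences and one instruction. Protocol 10.1 allows the SAP to be finalized up to database lock. Protocol 9.2.1 and 9.3.1 can stay as they are; rewriting them would be an amendment requiring ethics approval under Section 14.1. The downside is a slightly higher TEAE count in both arms.

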8.2 Concomitant Medications

All concomitant medications listed on the case report form will be provided in data listings in the clinical study report. Each medication will be mapped to their corresponding Preferred Term from the ATC-WHO-DD. A frequency distribution of all concomitant medications used during the study will be provided for each treatment group. Medications used prior to randomization but stopped prior to randomization will be summarized separately from those used concomitantly. A subject data listing will be provided.

8.3 Dry Eye History and Medical History

History terms will be classified according to the MedDRA system to the levels of SOC and primary PT.

An overall summary will be presented which gives the number and percentage of subjects within each treatment group that experienced each condition or procedure. A subject data listing will be provided.

8.4 Slit-Lamp Biomicroscopy

The observations from the Slit-Lamp Biomicroscopy will be summarized in frequency tables based on the Normal / Abnormal assessment at each visit for each measure. Shift tables (From: Normal/Abnormal To: Normal/Abnormal) will be provided for each individual assessment as a measure of change from baseline for each visit. A subject data listing will be provided.

8.5 Ophthalmoscopy/Dilated Fundoscopy

The observations from the Dilated Ophthalmoscopy exam will be summarized in frequency tables based on the Normal / Abnormal assessment at each visit for each measure separately. Shift tables (From: Normal/Abnormal To: Normal/Abnormal) will be provided for each individual assessment as a measure of change from baseline for each visit. A subject data listing will be provided.

8.6 Urine Pregnancy Test

A listing of urine pregnancy test results will be provided.

9. CHANGES FROM THE PROTOCOL

Four additional composite endpoints have been defined for analysis that were not defined in the protocol. These composite endpoint use both the STT and the FCS assessments and full details are set out in sections 7.5.4 and 7.6.2.

10. INTERIM ANALYSIS

No interim analyses are planned.

Table Number	Table Title	Population(s)
[REDACTED]	[REDACTED]	[REDACTED]

APPENDIX 1: SCHEDULE OF EVENTS

Visit	Visit 1 Screening	Visit 2 Pre- Randomizati on	Visit 2 Randomizati on	Visit 3 Treatment	Visit 4 Treatment	Visit 5 End of Treatment/ Early Term ¹	Visit 6 Follow-up ²
Day	Day -3 to -1		Day 1	Day 7 (±2 days)	Day 14 (±2 days)	Day 28 (±2 days)	Post- treatment FU (+3 days)
Informed Consent	✓						
Demography	✓						
Medical/Ophthalmic/ Surgical history	✓						
Eligibility Criteria Assessment	✓	✓					
Concomitant Medications Assessment	✓	✓		✓	✓	✓	✓
Urine Pregnancy Test ³	✓					✓	
SANDE		✓		✓	✓	✓	
Individual Symptom Severity Assessments using VAS		✓		✓	✓	✓	
BCVA	✓	✓		✓	✓	✓	✓
STT	✓				✓ ⁴	✓ ⁴	
Slit-Lamp Biomicroscopy		✓				✓	
FCS		✓		✓ ⁹	✓ ⁹	✓ ⁹	
Ophthalmoscopy (dilated)	✓						✓

Visit	Visit 1 Screening	Visit 2 Pre- Randomizati on	Visit 2 Randomizati on	Visit 3 Treatment	Visit 4 Treatment	Visit 5 End of Treatment/ Early Term ¹	Visit 6 Follow-up ²
Day	Day -3 to -1		Day 1	Day 7 (±2 days)	Day 14 (±2 days)	Day 28 (±2 days)	Post- treatment FU (+3 days)
OTC Ocular Lubricant Administration at the Study Site	✓	✓					
Randomization			✓				
IP Administration at the Study Site			✓ ⁵	✓	✓	✓	
Drop Discomfort Assessment at the Study Site		✓ ⁶	✓ ⁷	✓	✓	✓	
AE Assessment	✓	✓	✓	✓	✓	✓	✓
IP Dispensation			✓	✓	✓		
Dosing Diary and VAS Scales Dispensation			✓	✓	✓		
Subject Contact for Drop Discomfort Assessment			✓	✓	✓ ⁸		

Abbreviations: AE=Adverse event; BCVA= Best Corrected Visual Acuity; FCS= Fluorescein Corneal Staining; IP=Investigation Product; OTC=Over-the-counter; SANDE= Symptom Assessment and Dry Eye; STT=Schirmer Tear Test; VAS=Visual Analog Scale.

¹ Every effort should be made for subjects who withdraw from the study, either voluntarily or at the Investigator's discretion, to undergo end of study assessments (Visit 5).

² Visit 6 should be conducted 3 days after End of Treatment (+3 Day window).

³ For women of childbearing potential only.

⁴ STT should be performed at least 1 hour after IP instillation and at least 20 minutes after FCS.

⁵ IP instillation should be performed at least 2 hours after OTC ocular lubricant (Refresh Plus) instillation.

⁶ Post OTC ocular lubricant instillation.

⁷ Post IP instillation.

⁸ Subjects will be contacted by masked site staff the evening of the Visit 4 and in the evening prior to Visit 5.

⁹ FCS should be performed after the Drop Discomfort Assessment.
